2.6.2.6 Brain volume loss

The null hypothesis is that there is no difference in brain volume change between ofatumumab 20mg sc and teriflunomide 14 mg po

- Superiority of ofatumumab 20mg sc over teriflunomide 14 mg po will be concluded if there is less brain volume loss (positive difference in slope from the random coefficient model) in patients treated with ofatumumab compared with teriflunomide and the observed p-value for the between-treatment comparison is less than the two-sided significance level of 0.05. The multiplicity adjustment explained in [Section 2.5.3](#) applies.

Confirmatory analysis of brain volume loss: The percentage change from baseline in brain volume will be estimated on the basis of all scheduled scans up to the last available MRI scan that evaluated percentage brain volume change relative to baseline. A random coefficients model will be used as main analysis for this endpoint in order to adjust for the various length of follow-up time in this study. Brain volume change was approximately linear over time and approximately normally distributed in 3 independent studies of the fingolimod phase 3 program. The random coefficients model will include treatment, region as fixed effects (factors), and time, number of Gd-enhancing lesions at baseline, baseline T2 volume, and normalized brain volume at baseline as continuous covariates and treatment by time interaction. Time as a continuous covariate allows for estimation of different slopes and intercepts among treatment groups. The model will also contain random terms to account for deviations about the population slope and intercept. The statistical test will address the question whether there is a difference in the slope of brain volume change by treatment group. The annual rate of percent change from baseline in brain volume is approximates as the population slope within the treatment group. Since the random coefficients model allows for the estimation of different slopes and intercepts among the treatment groups, differences between treatments at any time can be summarized using this model. Model estimates of percentage brain volume change at Months 12 and 24 will be provided by treatment with corresponding 95% confidence interval. Treatment differences will be estimated at the same time points with confidence interval and a p-value for the test of a difference in slope.

Supportive analysis: Additionally, brain volume change and the annualized rate of brain atrophy (ARBA) will be summarized by visit. Calculation of ARBA is provided in [Section 2.7.1](#). Cross-sectional comparisons at each visit will be made using ANCOVA models with ARBA as the response variable, treatment and region as factors, number of Gd-enhancing lesions at

baseline, baseline T2 volume, and normalized brain volume at baseline as continuous covariate. Line plots of percentage brain volume change over time by treatment will be provided.

In addition, the percentage change from baseline in brain volume will be estimated on the basis of all scheduled scans up to the last available MRI scan that evaluated percentage brain volume change relative to baseline in a repeated measures model. The unstructured covariance matrix will be used. The model will include treatment and scanning time point as factors (Month 12 and Month 24), region, number of Gd-enhancing lesions at baseline, baseline T2 volume and normalized brain volume at baseline as covariates. For the purpose of this model, visit windows will be used to map all available MRI assessments to Months 12 (Week 48) and 24 (Week 96) as defined in [Table 2.5](#). The comparison of treatment differences in mean at Month 12 and 24 will be made using this model.

Percentage brain volume change is cumulative measure of disease activity. Since the percentage brain volume change is assessed relative to the MRI scan collected at screening (i.e. well before the start of study medication intake), it is expected that these analyses tend to underestimate the true treatment difference between study drugs.

2.6.3 Handling of missing values/censoring/discontinuations

2.6.3.1 Disability related endpoints (3mCDW, 6mCDW and 6mCDI)

Patients discontinuing study treatment should remain in the study and continue to follow the assessment schedule. The primary analysis of the time to 3-month/6-month confirmed disability worsening or the time to 6-month confirmed improvement uses all the available data up to the end of treatment epoch date, irrespective of on or off study treatment.

All patients in FAS will be included in the primary analysis. Patients who do not reach the endpoint by the end of treatment epoch date will be censored at date of last EDSS assessment during the treatment epoch. A per-protocol analysis of time to 3mCDW and time to 6mCDW will be performed to analyze on-treatment data (on-treatment period as defined in [Section 2.1.1](#)) from patients who have no major protocol deviations.

2.6.3.2 MRI endpoints

The primary analysis will use all available data up to the end of treatment epoch date, irrespective of on or off study treatment.

For the number of Gd-enhancing lesions and the number of new or enlarging T2 lesions, the primary NB model with an offset for the total number of scans or for the time from screening scan respectively adjusts for missing information (drop-out) under the assumption of non-informative drop-out, information is missing at random, and constant intensity (#lesion/time) of lesion formation over time.

For the percent change from baseline in brain volume, the primary analysis of random coefficient model will include longitudinal data from all scheduled post-baseline MRI scans as response. Under the assumption of linearity of the percentage brain volume change over time, the model corrects for missing values.

2.7 Analysis of secondary efficacy objective(s)

2.7.1 Secondary endpoints

Other secondary efficacy endpoints include:

- Time to first confirmed relapse: For patients with at least one confirmed relapse, the time to first confirmed relapse will be calculated as (start date of first confirmed relapse - date of first administration of study drug+1). For patients without confirmed relapses, they are censored with censored time as time in study (as defined in [Section 2.5.1](#)).
- ARR > 8 weeks after the onset of treatment (estimated from sensitivity analysis of primary endpoint) (details as described in [Section 5.5.3.1](#)).
- Risk of a 3mCDW > 8 weeks after the onset of treatment (estimated from sensitivity analysis of corresponding key secondary endpoint) (details as described in [Section 5.5.3.2](#)).
- Risk of a 6mCDW > 8 weeks after the onset of treatment (estimated from sensitivity analysis of corresponding key secondary endpoint) (details as described in [Section 5.5.3.2](#)).
- Time to 6-month confirmed cognitive decline on SDMT (6mCCD): similar to definition of 6mCDW ([Section 2.6.1.1](#)) but replacing the worsening criteria by at least an increase by 4 points from baseline in SDMT oral score. Patients who do not reach the endpoint by the end of treatment epoch date will be censored at date of last SDMT assessment during the treatment epoch.
- Time to 6mCDW or 6mCCD: defined as either a 6-month confirmed disability worsening, or a 6-month confirmed cognitive worsening, whichever is first. If a patient has both events achieved, time variables for this composite endpoint will be the same as the event occurred earlier. If 6mCDW is achieved but 6mCCD is not, the time variables for this composite endpoint will be the same as the time to 6mCDW event. If 6mCCD is achieved but 6mCDW is not, the time variables for this composite endpoint will be the same as the time to 6mCCD event. If neither events achieved, the patient is censored. The time variable will take the larger value in the censoring times corresponding to these 2 individual events.
- SDMT oral score by visit-window
- Time to 6-month confirmed worsening of at least 20% in the timed 25-foot walk test (T25FW): similar to definition of 6mCDW ([Section 2.6.1.1](#)) but replacing the worsening criteria by at least 20% increase from baseline in T25FW score. Patients who do not reach the endpoint by the end of treatment epoch date will be censored at date of last T25FW assessment during the treatment epoch.
- Time to 6-month confirmed worsening of at least 20% in the 9-Hole Peg Test (9HPT): similar to definition of 6mCDW ([Section 2.6.1.1](#)) but replacing the worsening criteria by at least 20% increase from baseline in 9HPT score in at least one hand. Patients who do not reach the endpoint by the end of treatment epoch date will be censored at date of last 9HPT assessment during the treatment epoch.

- 6mCDI sustained until EOS: same as 6mCDI except that the rest EDSS scores (scheduled or unscheduled) after the confirmation visit of the 6mCDI during the treatment epoch have to meet the disability improvement criteria as well.
- Disability status during the study (classified as improved, stable, or worsened): patients will be classified as improved if 6mCDI sustained until EOS was met (regardless whether 6mCDW status was met at an earlier time point); or classified as stable if 6mCDW was not met & 6mCDI sustained until EOS was not met; or classified as worsened if 6mCDW was met & 6mCDI sustained until EOS was not met.
- MS relapse characteristics include severity, recovery, hospitalization, and steroid treatment. The severity of MS relapses will be derived according to the criteria in [Table 2-15](#). All relapses (confirmed or unconfirmed) will be considered. For confirmed relapses, the EDSS used to confirm the relapse (as specified in [Section 2.5.2](#)) will be used to determine the severity. For unconfirmed relapses, all EDSS assessments taken within 30 days from the relapse start date and before the relapse end date will be checked among which the most severe case will be selected to determine the severity. If no such EDSS assessment is available, the severity will be set to “missing EDSS”. If none of such EDSS assessments meet the mild, moderate or severe conditions, the severity will be set to “no worsening in EDSS”.

Table 2-15 Severity of MS relapse

Mild relapse	Moderate relapse	Severe relapse
EDSS increase of 0.5 point	EDSS increase of 1 or 2 points	Exceeding Moderate criteria
or	or	or
1 point FS change in one to three systems	2-point FS change in one or two systems	Exceeding Moderate criteria
	or	or
	1-point change in four or more systems	Exceeding Moderate criteria
Definition is based on the EDSS obtained to confirm the relapse as compared to the last EDSS (scheduled or unscheduled) taken in the absence of (confirmed or unconfirmed) relapse and prior to the current relapse. EDSS refers to total score; FS refers to functional score; all of the 7 functional scores are considered in this derivation.		

[\[Panitch et al 2002\]](#)

- ARR time-based and ARR patient based: ARR using a “time-based approach” are calculated by taking the total number of relapses observed for all patients within a treatment group divided by the total number of days in study of all patients within the treatment group and multiplied by 365.25 days. Also a “patient-based approach” is presented, where individual ARRs are computed and summarized over patients within a treatment group. For above ARR calculations, one analysis will consider confirmed relapses only. Another analysis will consider both confirmed and unconfirmed relapses together. T2 lesion volume and its change from baseline MRI scans by visit-window

- Number of new or enlarging T2 lesions on MRI between Month 12 and EOS: The number of new T2 lesions on the EOS scan relative to the Month 12 scan will be collected; The time (in years) from the Month 12 scan to the EOS MRI scan will be calculated as (date of EOS MRI scan – date of Month 12 MRI scan +1)/365.25.
- Number of new or enlarging T2 lesions on MRI at yearly visits relative to screening scan: The number of new T2 lesions at yearly visit scans relative to the screening scan will be collected; The time (in years) from the screening scan to the yearly MRI scan will be calculated as (date of yearly MRI scan – date of screening MRI scan +1)/365.25.
- Annualized rate of brain atrophy (ARBA) by visit-window: ARBA describes the “averaged annual percentage change” in brain volume. It is designed to adjust for differences in the time spent between two scans that are compared by standardizing the percentage change in brain volume (PBVC) to 1 year. The logic of interest rates applies. $ARBA = [(PBVC/100+1)^{(365.25/days)}-1]*100$, where “PBVC” represents the percentage brain volume change obtained between 2 scans and “days” stands for the number of days between the two scans that are being compared. Days are calculated as post-baseline MRI scan date – screening MRI scan date +1.
- Proportion of patients free of clinical and MRI disease activity (No evidence of disease activity; NEDA-4): NEDA-4 is defined as no 3mCDW, no confirmed MS relapse, no new or enlarging T2 lesions on any MRI scan (scheduled or unscheduled) compared to baseline, and brain volume change $>-0.4\%/year$ on all MRI scans (scheduled and unscheduled; brain volume as measured by ARBA). The main analysis will consider only those patients who were followed-up to the assessment time point in the analysis (e.g. only patients with ≥ 12 months of follow-up in the 12-month assessment of disease freedom, etc.). Intermediate missing values (e.g. due to missing MRI assessments) will be considered not free of disease activity. For the derivation of NEDA-4, data up to day 365.25 will be considered in the year 1 analysis and data up to day 730.5 will be considered in the year 2 analysis.
- EDSS total score by visit-window
- The 25-foot Timed Walking Test (T25FW) score by visit-window: two trials will be performed at each scheduled visit. The average scores of the two trials per visit will be calculated as $T25FW_{score} = \frac{1}{2}(T25FW_1 + T25FW_2)$. In case of missing data, the average of the non-missing values will be taken.
- The 9-Hole Peg Test (9HPT) score by visit-window: four trials (two of each arm) will be performed at each scheduled visit. The 9HPT score per visit will be calculated for the dominant and the non-dominant hands separately and then for the average of both hands. In case of missing data, the average of the non-missing values will be taken.
 - $9HPT_{dominant\ hand} = (9HPT_{dominant\ hand, trial\ 1} + 9HPT_{dominant\ hand, trial\ 2})/2$
 - $9HPT_{non-dominant\ hand} = (9HPT_{non-dominant\ hand, trial\ 1} + 9HPT_{non-dominant\ hand, trial\ 2})/2$
 - $9HPT_{total} = (9HPT_{non-dominant\ hand} + 9HPT_{dominant\ hand})/2$.
- NfL related secondary hypotheses are specified in [Section 2.6.2.5](#) as ‘supportive analysis’ for the key-secondary endpoint NfL.

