2.2 Secondary objective(s)

Key secondary objectives

All disability-related key-secondary objectives will be addressed in the combined data (meta-analysis) from this study and the second study of identical design. All other objectives will be addressed based on the data from this study alone.

The key secondary objectives are to evaluate if ofatumumab 20 mg sc q4 weeks is superior to teriflunomide 14 mg po once daily on the following efficacy measures:

- Time to disability worsening as measured by 3-month confirmed worsening (3mCDW) on The Expanded Disability Status Scale (EDSS)
- Time to disability worsening as measured by 6-month confirmed worsening (6mCDW) on EDSS
- Time to disability improvement as measured by 6-month confirmed improvement (6mCDI) on EDSS
- Number of T1 Gd-enhancing lesions per MRI scan
- Number of new or enlarging T2 lesions on MRI per year (annualized T2 lesion rate)
- Neurofilament light chain (NfL) concentration in serum
- Rate of brain volume loss (BVL) based on assessments of percentage brain volume change from baseline

Other secondary objectives

Evaluate if ofatumumab 20 mg sc q4 weeks is superior to teriflunomide 14 mg po once daily on the following efficacy measures:

- Time to first relapse
- Annualized relapse rates > 8 weeks after the onset of treatment
- Risk of a 3mCDW > 8 weeks after the onset of treatment
- Risk of a 6mCDW > 8 weeks after the onset of treatment
- Time to a 6-month confirmed cognitive decline (6mCCD), defined as a 4-point worsening on Symbol Digit Modalities Test (SDMT)
- Time to 6mCDW or 6mCCD, whichever is reached first
- Change in cognitive performance relative to baseline as measured by the SDMT
- Time to 6-month confirmed worsening of at least 20% in the timed 25-foot walk test (T25FW)
- Time to 6-month confirmed worsening of at least 20% in the 9-hole peg test (9HPT)
- Time to 6mCDI sustained until End of Study (EOS) as measured by EDSS
- Number of new or enlarging T2 lesions between Month 12 and EOS
- Change in T2 lesion volume relative to baseline
- Proportion of patients with no evidence of disease activity (NEDA-4; defined in [Section 9.5.1.2](#)) at year 1 and 2
- Physical and psychological impact of MS disease as measured by the Multiple Sclerosis Impact Scale (MSIS-29)

[figure not shown]
In the subgroup of newly diagnosed, treatment-naïve patients, evaluate if:

- High NfL (above median) concentration at baseline is predictive of higher disease activity post baseline

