6.4.7 Symbol Digit Modalities Test (SDMT)

The SDMT will be assessed according to the schedule in [Table 6-1](#). The SDMT is a sensitive and specific test to assess processing speed which is typically affected in cognitive impaired MS patients ([Benedict et al. 2017](#)). During the administration of the SDMT only the examiner and the patient should be in the testing room. The SDMT will be administered according to standardized instructions by the Investigator or another qualified health care professional experienced with the administration of the SDMT (refer to [Section 5.6.6](#)). Patients are presented with a test instrument at the top of which is a row of nine numbers paired with unique symbols. Below this part of the test instrument is an array of symbols paired with empty spaces, the patient's task is to verbally match the number for each symbol as rapidly as possible. The SDMT incorporates a number of practice items at the start of each test to familiarize the patient (these results are not included in the final score). The test takes approximately 5 minutes to administer.

Alternate versions of the SDMT will be used in an alternating pattern to minimize learning effects. The test scoring is calculated based on the number of correct answers in 90 seconds.

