1.2.3 Other secondary objectives

Evaluate if ofatumumab 20 mg sc q4w is superior to teriflunomide 14 mg po once daily on the following efficacy measures:

[figure not shown]
- Time to first relapse
- Annualized relapse rates > 8 weeks after the onset of treatment
- Risk of a 3mCDW > 8 weeks after the onset of treatment
- Risk of a 6mCDW > 8 weeks after the onset of treatment
- Time to a 6-month confirmed cognitive decline (6mCCD), defined as a 4-point worsening on Symbol Digit Modalities Test (SDMT)
- Time to 6mCDW or 6mCCD, whichever is reached first
- Change in cognitive performance relative to baseline as measured by the SDMT
- Time to 6-month confirmed worsening of at least 20% in the timed 25-foot walk test (T25FW)
- Time to 6-month confirmed worsening of at least 20% in the 9-hole peg test (9HPT)
- Time to 6mCDI sustained until the EOS as measured by EDSS
- Number of new or enlarging T2 lesions between Month 12 and EOS
- Change in T2 lesion volume relative to baseline
- Proportion of patients with no evidence of disease activity (NEDA-4; defined in [Section 2.7.1](#)) at year 1 and 2
- Physical and psychological impact of MS disease as measured by the MSIS-29

In the subgroup of newly diagnosed, treatment-naïve patients, evaluate if:

- High NfL (above median) concentration at baseline is predictive of higher disease activity post baseline
- Patients with a high NfL (above median) concentration at baseline benefit from a stronger relative treatment effect of ofatumumab vs teriflunomide
- The safety profile of ofatumumab vs teriflunomide is comparable in patients with high NfL (above median) concentration at baseline

Evaluate the safety and tolerability of ofatumumab 20 mg sc q4w compared to teriflunomide 14 mg po once daily

Evaluate the pharmacokinetics (PK) of ofatumumab

2 Statistical methods

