2.5 Analysis of the primary objective

2.5.1 Primary endpoint

The primary endpoint is the annualized relapse rate (ARR), which is defined as the number of confirmed MS relapses in a year. In the primary analysis, the ARR is estimated based on the FAS which follows the intent-to-treat principle in a negative binomial (NB) model by using individual relapse count as the response variable with natural log of time in study in years as an offset variable.

Two variables are required for the calculation of the ARR (excluding covariates):

- The cumulative number of confirmed MS relapses by patient is the response variable in the negative binomial model. All confirmed relapses with a start date on or after the date of first administration of study drug and prior to or on the end of treatment epoch date will be included in the analysis. Additional details are provided in [Section 5.1.3.4](#).
 - The definition of a confirmed MS relapse is one accompanied by a clinically relevant change in the EDSS assessment, i.e. an increase of at least 0.5 points on the EDSS (total) score, or an increase of at least 1 point on at least two Functional scores (FSs), or an increase of at least 2 points on at least one FS, excluding changes involving bowel/bladder or cerebral FS, compared to the last EDSS assessment taken in the absence of (confirmed or unconfirmed) relapse and prior to the current relapse. EDSS obtained on the date as indicated on the Summary of MS Relapse eCRF page will be used. If such EDSS assessment is missing or not meeting the criteria to confirm the relapse, all other EDSS assessments taken within 30 days from the relapse start date (i.e., EDSS assessment date – relapse start date ≤ 30) and before the relapse end date (EDSS assessment date < relapse end date) will be checked. If at least one of such available EDSS assessments meets the criteria, the relapse is a confirmed relapse. Otherwise, the relapse is considered an unconfirmed relapse.
- The time in study by patient will be used as an offset variable to adjust for the various length patients have been observed and at-risk of a confirmed MS relapse in the study. Time in study for ARR will be calculated as (end of treatment epoch date – first dose date+1)/365.25.

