Additionally, the time-to-first relapse will be analyzed in a Cox proportional hazards model on the FAS. In comparison with the primary analysis in a negative binomial model, the Cox proportional hazards model does not assume constant relapse rates (but rather it assumes proportional hazards). The Cox proportional hazards model will be specified with treatment, region, number of relapses in previous year, baseline EDSS, baseline number of T1 Gd-enhancing lesions and the patient's age at baseline as covariates. For patients with at least one relapse, the time to first relapse will be calculated as (start date of first relapse - date of first administration of study drug+1). For patients without relapses, they are censored with censored time as time in study (as defined in [Section 2.5.1](#)).

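### SAP 2.7.1 counts a 4-point SDMT gain as cognitive decline and censors time to first relapse in years while timing events in days, so three secondary endpoints are wrong as written

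*SAP*

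**What the plan says.** **Cognitive decline.** SAP 1.2.3 lists 6mCCD as "defined as a 4-point worsening on Symbol Digit Modalities Test (SDMT"), and Protocol 2.2 words it the same way. The operative derivation is in SAP 2.7.1. It takes the 6mCDW definition, "replacing the worsening criteria by at least an increase by 4 points from baseline in SDMT oral score". Protocol 6.4.7 gives the scoring: "The test scoring is calculated based on the number of correct answers in 90 seconds". The composite in SAP 2.7.1 is "defined as either a 6-month confirmed disability worsening, or a 6-month confirmed cognitive worsening, whichever is first", so its cognitive part comes from the same rule.

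**Time to first relapse.** For a patient with a confirmed relapse, SAP 2.7.1 takes the relapse start date minus the first dose date plus 1, with no division. For the others, "For patients without confirmed relapses, they are censored with censored time as time in study", with a cross-reference to SAP 2.5.1. There the only formula for time in study is the end of treatment epoch date minus the "first dose date+1)/365.25". SAP 2.5.5, which sets up the Cox model as a supportive analysis of the primary endpoint, has the same construction: "For patients without relapses, they are censored with censored time as time in study".

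**The concern.** A higher SDMT score is better, so the rule in SAP 2.7.1 flags sustained improvement as decline. If ofatumumab preserves or improves cognition, more ofatumumab patients would meet the event definition, and a benefit would be reported as a hazard ratio above 1. A patient whose score only falls would never be a 6mCCD event. That patient would enter the composite only by also reaching 6mCDW.

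The second problem is one of units. If event times are in days and censoring times in years, relapse-free patients leave the risk set almost at once. The Cox model then compares relapsers with other relapsers and loses nearly all information on who relapses at all. This analysis is an other-secondary endpoint. Protocol 9.4.3 also offers it as a check that does not need the constant relapse rate assumed by the primary negative binomial model. Run literally, it could appear to contradict a positive ARR result.

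**Working it through.** The documents give no event count or power for these three endpoints, so there is no planned figure to reproduce. The definitions can be checked by substitution.

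**1. SDMT direction.** Event under SAP 2.7.1: score minus baseline ≥ +4. Event under the objective (4-point worsening of a correct-answer count): score minus baseline ≤ −4.

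| Baseline → follow-up (confirmed) | Change | SAP 2.7.1 | Stated objective |
|---|---|---|---|
| 50 → 54 | +4 | event | no event |
| 50 → 46 | −4 | no event | event |

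No score change satisfies both rules. The neighbouring rules for T25FW and 9HPT also use an increase. They are correct, because those tests are timed in seconds (Protocol 6.4.5 and 6.4.6).

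The documents give no distribution of SDMT change, so the share of patients affected can only be illustrated. Normal tail areas at a single visit, ignoring the 6-month confirmation, are:

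| Assumed change (mean, SD) | Gain ≥ 4 | Loss ≥ 4 |
|---|---|---|
| −1, 8 | 27% | 35% |
| 0, 8 | 31% | 31% |
| +2, 8 | 40% | 23% |

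The wrong event set may be smaller or larger than the right one. In every case it consists of the wrong patients.

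**2. Units for time to first relapse.** Putting numbers into the SAP formulas:

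- Relapse starting on day 56: event time 56.
- Relapse-free and followed 548 days: censored at 548/365.25 = 1.50.
- Relapse-free and followed 913 days (the 30-month maximum): censored at 913/365.25 = 2.50.

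Every relapse from day 3 onward is therefore evaluated in a risk set made up only of patients who relapse.

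**3. Size of the unit effect.** The relapse inputs come from SAP 3.1.1: annual rates 0.168 and 0.28, dispersion κ = 0.82, and T = 1.5 years for the sample size. As a check on these inputs, the sample-size formula n = (z₀.₉₇₅ + z₀.₉₀)² × [1/(λ₁T) + 1/(λ₂T) + 2κ] / (ln 0.6)² gives 321.7, that is 322 per arm, which matches the plan.

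First-relapse times were then simulated as exponential, with patient rate equal to the arm rate times a gamma variable of mean 1 and variance 0.82. There were 450 patients per arm, 200 replicates, and an unadjusted Cox model with Efron ties. Follow-up was taken as uniform over 1 to 2 years, which is an assumption. Power means two-sided p < 0.05 in favour of ofatumumab.

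| Units | Median HR | Power |
|---|---|---|
| Days for events and censoring | 0.63 | 92% |
| As written (days and years) | 0.96 | 4% |

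About 25% of patients relapsed, and about 99.5% of first relapses fell after day 2. With equal rates of 0.28 in both arms, the as-written analysis also favoured ofatumumab in 4% of replicates, so in this run it detected the effect no more often than chance.

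Further runs, with follow-up uniform over 1 to 2 or 1 to 2.5 years or fixed at 1.5 years, gave HR 0.63 to 0.65 and power 90% to 97% with consistent units. As written they gave HR 0.92 to 0.96 and power 4% to 9%. With 200 replicates the simulation error at 92% power is √(0.92 × 0.08/200) ≈ 2 percentage points.

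**The case against.** **The SDMT wording is a drafting slip.** The protocol and SAP 1.2.3 both say worsening, and SAP 2.7.1 itself calls the endpoint cognitive decline. SAP Section 4 lists no change to it, and the wording probably follows the T25FW and 9HPT rules beside it. Programmers may well have implemented the intended direction. All of this is plausible, but 2.7.1 is the derivation text and it contradicts the objective. Programming that departs from it silently leaves the reported endpoint without a matching prespecified definition.

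**Time in study is also used in days.** The formula in years is labelled as being for ARR. SAP 5.5.3.1.1 speaks of a time in study greater than 56 days, and subtracts 56 before dividing by 365.25. This is good evidence of intent. However, Table 5-5 in the same section shows total time in study as 100/365.25, so usage is mixed. The censoring rule points explicitly to Section 2.5.1, whose only formula is in years.

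**The sizes rest on assumptions.** This stands for the SDMT percentages, which have no source in the documents and ignore confirmation. The simulated loss of power is what follows from literal implementation. It is not a forecast, because a programmer would probably notice censoring times below 3.

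**The impact is limited.** This also stands. All three are other-secondary endpoints outside the testing procedure in SAP 2.5.3, and only one of the composite's two components is reversed.

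**Conclusion.** Both errors hold as written. The 6mCCD rule in SAP 2.7.1 has the wrong sign, which makes 6mCCD and the cognitive part of the composite the opposite of the objective. Time to first relapse mixes days and years in SAP 2.5.5 and 2.7.1. Three secondary time-to-event endpoints are affected; ARR and the key secondary tests are not.

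The reversed SDMT direction follows from the text alone and needs no assumption. The unit mismatch follows from the cross-reference to SAP 2.5.1. Its effect, a hazard ratio moving from about 0.63 to 0.92–0.96 with power falling from at least 90% to below 10%, depends on the plan's relapse assumptions and an assumed follow-up pattern. The loss appeared under every pattern tried. The text must be corrected, because following it literally changes the results.

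**What to change.** - In SAP 2.7.1, define the 6mCCD criterion as a decrease of at least 4 points from baseline in the SDMT oral score. The composite then needs no edit of its own.
- In SAP 2.5.5 and 2.7.1, censor relapse-free patients at (end of treatment epoch date − first dose date + 1) in days, and drop the cross-reference to the time in study of Section 2.5.1.
- Check the derivation specifications and any outputs already produced for SDMT direction and time unit, and document the result.

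The cost is a few sentences plus that check. The SAP history ends with an addendum dated after database lock, so a correction to this version would also be a post-lock addendum. That addendum corrected the B-cell depletion definition, so the route has been used before. No new data or change in design is needed.
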